7.2.2 Intervention Delivery

Interventions 1 and 2 will be operationalized through an interruptive clinical decision support tool, triggered within the electronic health record whenever a respiratory culture is ordered in a mechanically-ventilated study ICU patient. Intervention 3 will be operationalized through modifications in Clinical Laboratory workflows.

8 END-OF-INTERVENTION/END-OF-STUDY

8.1 DISCONTINUATION OF INTERVENTION

The full diagnostic stewardship intervention will be discontinued at the primary study completion date (February 2023). The study interventions will also be halted for prespecified increases in adverse safety outcomes (noted previously).

9 STATISTICAL CONSIDERATIONS

9.1 GENERAL STATISTICAL APPROACH

9.1.1 Descriptives

We will compare categorical variables by reporting frequencies and percentages and assess statistical significance using a chi-square test. Subject-level continuous variables will be compared using Kruskal-Wallis tests. Rate variables (e.g., deaths per 1,000 MVPDs) will be compared using a z-score test.

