4 OBJECTIVES AND ENDPOINTS

OBJECTIVES	ENDPOINTS	JUSTIFICATION FOR ENDPOINTS
Primary		
To determine the safety of a multi-faceted ventilator-associated pneumonia diagnostic stewardship bundle.	
Mortality per 1000 mechanically-ventilated patient days
 
Ventilator-associated events (using Centers for Disease Control/National Healthcare Safety Network definitions) per 1000 patient days
 
Median duration of mechanical ventilation per patient.
	The goal of this study is to demonstrate preliminary safety of a diagnostic stewardship bundle for ventilator-associated pneumonia.
Secondary		
To determine the association between a multi-faceted ventilator-associated pneumonia diagnostic stewardship bundle and ICU antibiotic utilization rates.	
Total ICU antibiotic utilization rates (total antibiotic days of therapy per 1000 mechanically-ventilated patient days).
 
Broad-spectrum ICU antibiotic utilization rates (broad-spectrum antibiotic days of therapy per 1000
	Our preliminary data suggests that a bundled diagnostic stewardship intervention can successfully reduce antibiotic use in mechanically-ventilated patients.

OBJECTIVES	ENDPOINTS	JUSTIFICATION FOR ENDPOINTS
	mechanically-ventilated patient days).	
To determine the association between a multi-faceted ventilator-associated pneumonia diagnostic stewardship bundle and rates of positive respiratory cultures.	Positive respiratory cultures per 1000 mechanically-ventilated patient days.	
To assess study feasibility and adherence to protocolized intervention.	Respiratory cultures ordered per 1000 mechanically-ventilated patient days Percentage of respiratory cultures obtained by BAL Percentage of respiratory cultures from BAL samples with alveolar neutrophils <50%	Adherence to study intervention is crucial to evaluating study efficacy and potentially recalibrating approach to intervention prior to multi-center implementation.

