6 STUDY POPULATION

6.1 INCLUSION CRITERIA

This pilot/feasibility trial will occur within the Michigan Medicine Cardiac Care Unit (CCU, 7D) and the Michigan Medicine Critical Care Medicine Unit (CCMU, 6D). This study will not be screening or enrolling individual patients, but rather instituting system-based interventions in the diagnostic testing workflow that providers engage with as part of routine clinical care. Study subjects in this trial are therefore all patients hospitalized in the aforementioned Michigan Medicine ICUs during the study period requiring invasive mechanical ventilation, as well as healthcare providers providing care to said patients in the aforementioned ICUs during the study period.

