9.1.2 Hypotheses

The primary study hypothesis was that implementation of a bundled DSI targeting the respiratory culturing pathway would not associate with significant increases in adverse safety outcomes.

The secondary study hypotheses were that implementation of a bundled DSI targeting the respiratory culturing pathway would associate with reductions in rates of respiratory culture positivity (RCP) and ICU-antimicrobial utilization rates (ICU-AURs).

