9.2 ANALYSIS OF THE PRIMARY AND SECONDARY ENDPOINT(S)

Primary and secondary study outcomes will be compared between patient cohorts before and after DSI implementation. All primary/secondary study outcomes will compare patients admitted to study ICUs over the course of the year-long study intervention (Feb 2022-23) versus those admitted in the pre-intervention historical control period (Feb 2017-22). As above, rate variables will be compared using a z-score test. A p-value of 0.05 will be utilized for statistical significance.

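### The plan does not say how deaths on the ventilator enter the median-duration safety endpoint, and on the default reading excess early deaths can leave it unchanged or improved

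*Combined protocol and SAP*

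**What the plan says.** Section 4 lists three primary safety endpoints. Two matter here: "Median duration of mechanical ventilation per patient" and "Mortality per 1000 mechanically-ventilated patient days". The third is ventilator-associated events. Section 6.1 sets the population as "all patients hospitalized in the aforementioned Michigan Medicine ICUs during the study period requiring invasive mechanical ventilation", with no division by survival.

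Section 9.1.1 gives the tests: "Subject-level continuous variables will be compared using Kruskal-Wallis tests", and "Rate variables (e.g., deaths per 1,000 MVPDs) will be compared using a z-score test". Section 9.2 compares the intervention year (Feb 2022-23) with the five preceding years and adds that "A p-value of 0.05 will be utilized for statistical significance". The primary hypothesis in section 9.1.2 is that the bundle "would not associate with significant increases in adverse safety outcomes". No margin is given.

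Section 9.4.1 puts the same median, by ICU, before the DSMB every two months. An increase of more than 2 standard deviations over the historical data in any one safety outcome halts the study. A decrease of more than 2 standard deviations is described as favourable, and the intervention continues.

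No section says what happens to the duration of a patient who dies while ventilated. There is no rule that death ends the duration, no restriction to survivors, no censoring, no worst rank, no ventilator-free days and no competing-risk method.

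**The concern.** The Kruskal-Wallis test is valid for two groups. The difficulty is the quantity being ranked. If observed ventilator days are used for everyone, a patient who dies on day 3 and a patient extubated on day 3 have the same value. Section 3.1.1 names underdiagnosis of a condition with substantial mortality as the main risk, so death is a foreseeable route of harm, and it is the route that this endpoint can register as improvement.

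The mortality endpoint has the complementary limitation. Its denominator is ventilated days, so if patients stay ventilated longer at an unchanged daily risk, more of them die and the rate does not move. No listed primary endpoint or DSMB metric reports deaths per patient. At stake is whether the safety tables can be read correctly, in particular whether a shorter or unchanged median is taken as reassurance beside an equivocal mortality rate.

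**Working it through.** **Inputs.** The documents give no death rate, liberation rate, ventilation duration or sample size, so there is no figure of the plan's to reproduce. Every hazard below is an assumption chosen to show direction and rough size.

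**Default reading.** Section 6.1 includes all ventilated patients. Section 9.3 (exploratory) gives every subject a denominator of days on the ventilator. A per-patient median over that population most naturally uses observed days, with death ending the count. This is an inference, not a stated rule.

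**Formulas.** Let liberation and death on the ventilator have constant daily hazards l and d:
- median duration = ln 2 / (l + d)
- mean duration = 1 / (l + d)
- deaths per 1000 ventilated days = 1000 × d
- deaths per patient = d / (l + d) = daily death rate × mean duration

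| Scenario | l | d | Median (days) | Deaths per 1000 days | Deaths per patient |
|---|---|---|---|---|---|
| Baseline | 0.10 | 0.025 | 0.693/0.125 = 5.5 | 25 | 0.025/0.125 = 20% |
| A. Death hazard up | 0.10 | 0.0375 | 0.693/0.1375 = 5.0 | 37.5 | 27% |
| B. Death up, liberation slower | 0.09 | 0.035 | 0.693/0.125 = 5.5 | 35 | 28% |
| C. Liberation slower only | 0.08 | 0.025 | 0.693/0.105 = 6.6 | 25 | 24% |
| D. Both slightly worse | 0.09 | 0.0275 | 0.693/0.1175 = 5.9 | 27.5 | 23.4% |

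In A the median improves and in B it is flat, while the mortality rate rises by 50% and 40%. In C the mortality rate is flat while the median rises by 19%. In D the rate rises by 10% (27.5/25) and the median by 6% (0.125/0.1175 = 1.064), but deaths per patient rise by 17% (1.10 × 1.064 = 1.17).

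**Range by simulation.** Assumed: baseline median 5 days; 20%, 30% or 40% dying on the ventilator; death hazard ratio 1.25 or 1.5; 2500 patients before and 500 after; two-sided 0.05; 1000 runs per scenario.
- Death hazard up alone: the median falls to between 4.76 and 4.17 days. Kruskal-Wallis on raw duration is significant for shorter ventilation in 14% to 89% of runs and for longer in at most 0.3%. With deaths ranked worst, the same test is significant for harm in 11% to 75%.
- Death hazard up and liberation slowed to match: the median stays at 5.00. In one case (30% baseline deaths, death hazard ratio 1.5, liberation hazard ratio 0.79) deaths on the ventilator rise from 30% to 45%. Raw Kruskal-Wallis is significant in 4% to 6% of runs, both directions together. With deaths ranked worst, it shows harm in 39% to about 100%.
- Across all these scenarios, the separate z test on deaths per ventilated day detects the increase in 57% to about 100% of runs. That is the final comparison, not the 2-standard-deviation halting rule.

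**The case against.** The strongest reply is that mortality is its own primary endpoint with its own test, and that the halting rule acts on any outcome, so a neutral or shorter median cannot cancel a mortality signal. This largely stands. In each of A to D at least one of the two endpoints moves in the harmful direction. Under constant hazards this must be so: deaths per patient equal the daily rate times the mean duration, and the mean is the median divided by ln 2, so if neither the rate nor the median rises, deaths per patient cannot rise. What remains is dilution, as in D, where neither endpoint shows the full rise in deaths per patient.

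A reader might infer that the plan counts death as the end of ventilation. The documents do not say so. A survivors-only median is also compatible with the text, and it would bring a different selection bias.

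A reader might also infer that more deaths always shorten the median. They do so only if they occur before the median, in patients who would otherwise have stayed ventilated beyond it. Deaths after the median leave it where it was. The constant-hazard model produces the shortening by construction.

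Finally, this is a pilot seeking preliminary safety, and competing-risk reporting may look like a preference. But the addition needs only duration and vital status, and it answers a question that the listed endpoints leave open.

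**Conclusion.** The concern holds in a limited form. The handling of death in a primary safety endpoint is undefined. On the most natural reading, that endpoint taken alone can look neutral or better while mortality rises, and section 9.4.1 would label a fall of more than 2 standard deviations favourable. The per-day mortality rate in turn misses deaths that arise only through longer ventilation.

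The documents do not support the stronger conclusion that a harmful bundle would pass the safety assessment as a whole. The mortality endpoint and the any-outcome halting rule remain, and in the modelled cases the two endpoints never both miss the harm. The remaining loss is dilution when harm is split: in the illustration, 10% and 6% on the listed measures against 17% in deaths per patient. These sizes rest on assumed constant hazards and cannot be derived from the documents. Outside that model, the identity involves the mean rather than the median.

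**What to change.** - In sections 9.1.1 and 9.2, state how a death on the ventilator enters the duration endpoint.
- Keep the listed endpoints and their tests.
- Add to the primary analysis and the DSMB tables the proportion of ventilated patients who die, and the cumulative incidence of liberation from ventilation with death as a competing event. Duration by survival status is a simpler alternative to the latter.
- State that a shorter median is not read as favourable without these figures beside it.

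The additions use ventilation duration and vital status, which the existing endpoints already require. The cost is a short text change and one more table. The halting rule need not change for this point.

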1 PROTOCOL SUMMARY

1.1 SYNOPSIS

[figure not shown]
Title:	Implementation of a Diagnostic Stewardship Bundle for Ventilator-associated Pneumonia among Mechanically-ventilated patients: a pilot/feasibility trial.
Grant Number:	Not applicable
Study Description:	A pilot/feasibility trial to evaluate the safety and efficacy of a multi-faceted ventilator-associated pneumonia diagnostic stewardship bundle. Trial ICUs will sequentially implement interventions targeting the respiratory culture diagnostic testing pathway to minimize diagnostic error and overtreatment of ventilator-associated pneumonia.
Objectives:	
Primary Objective: To determine the safety of a multi-faceted ventilator-associated pneumonia diagnostic stewardship bundle.
 
Secondary Objectives:
 
- To determine the association between a multi-faceted ventilator-associated pneumonia diagnostic stewardship bundle and ICU antibiotic utilization rates.- To determine the association between a multi-faceted ventilator-associated pneumonia diagnostic stewardship bundle and rates of positive respiratory cultures.
Endpoints:	To assess study feasibility and adherence to protocolized intervention.
	
Primary Endpoints:
 
- Mortality per 1000 mechanically-ventilated patient days- Ventilator-associated events (using Centers for Disease Control/National Healthcare Safety Network definitions) per 1000 patient days- Median duration of mechanical ventilation per patient.
	
Secondary Endpoints:
 
- Positive respiratory cultures per 1000 mechanically-ventilated patient days.- Total ICU antibiotic utilization rates (total antibiotic days of therapy per 1000 mechanically-ventilated patient days).- Broad-spectrum ICU antibiotic utilization rates (broad-spectrum antibiotic days of therapy per 1000 mechanically-ventilated patient days).- Respiratory cultures ordered per 1000 patient days.- Percentage of respiratory cultures obtained by BAL.- Percentage of respiratory cultures from BAL samples with alveolar neutrophils <50% (for Phase 2 only)
Study Population:	All mechanically-ventilated patients hospitalized within Michigan Medicine Cardiac Care Unit (CCU) and Critical Care Medicine Unit (CCMU).

Phase or Stage:	Pilot/feasibility trial of a population-based intervention.
Description of Sites/Facilities Enrolling Participants:	2 Michigan Medicine Intensive Care units.

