2.2 STUDY BACKGROUND

Antibiotic overuse is an increasingly recognized problem in intensive care units (ICUs).^{9,14} A recent multinational point-prevalence study of 1150 ICUs determined that 70% of patients surveyed were receiving antibiotics; only 54% of these patients had suspected or proven infection and only 35% had positive microbiologic cultures supporting a definitive diagnosis of infection.¹⁵ Excess antibiotic use catalyzes the acquisition and spread of multidrug-resistant organisms (MDROs), which have risen precipitously within ICUs in recent decades and are associated with excess morbidity, mortality, and healthcare expense.¹⁶⁻²³ Antibiotic overuse is also associated with adverse patient outcomes, including *Clostridioides difficile* infection, drug toxicity, and incident sepsis, as well as increases in healthcare costs and length of stay.²⁴⁻²⁸

Treatment for suspected respiratory infection—in particular, ventilator-associated pneumonia (VAP)—accounts for 50-70% of antibiotic use within ICUs.⁶⁻⁹ **Multidisciplinary case review and autopsy studies demonstrate that a substantial number of ICU patients treated for VAP are misdiagnosed, resulting in significant antimicrobial overuse.**^{10-13,29,30} For example, a multidisciplinary review of 231 cases diagnosed and treated as VAP in 6 ICUs at Johns Hopkins Hospital determined that antibiotics were not indicated in 59% of cases at the time of diagnosis, resulting in 1,183 days of unnecessary antibiotic use over 1 year.¹⁰ A similar multidisciplinary review of surgical ICUs at Johns Hopkins Hospital found that fewer than 25% of patients empirically treated for postoperative VAP met standardized criteria for infection, accounting for 1,460 days of inappropriate antibiotic therapy over 1 year.¹¹ At Michigan Medicine University Hospital, a review of patients with positive respiratory cultures who were treated for nosocomial pneumonia determined that 34% were misdiagnosed, account for a median of 12 excess days of unnecessary antibiotics per patient.³⁰

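### Read as a pooled Poisson comparison, the 9.2 z-score test has no valid standard error for the two antibiotic days-of-therapy rates, and the documents do not show which way the error runs

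*Combined protocol and SAP*

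**What the plan says.** Section 9.1.1 sets one method for all rates: "Rate variables (e.g., deaths per 1,000 MVPDs) will be compared using a z-score test". Section 9.2 carries it to the primary and secondary outcomes ("As above, rate variables will be compared using a z-score test") and adds: "A p-value of 0.05 will be utilized for statistical significance". The comparison is one intervention year (February 2022–23) against five control years (February 2017–22).

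Two of the secondary rates are antibiotic measures: "total antibiotic days of therapy per 1000 mechanically-ventilated patient days" and "broad-spectrum antibiotic days of therapy per 1000 mechanically-ventilated patient days" (Synopsis 1.1; also Section 4). Lower ICU antimicrobial use is a stated secondary hypothesis in 9.1.2.

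Neither 9.1.1 nor 9.2 gives a variance formula or a unit of analysis, and neither says whether the test is one- or two-sided. The documents do not say whether two agents given on the same day count as one DOT or two.

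Section 9.3 plans a subject-level negative binomial model and a monthly interrupted time series for antibiotic use, both as exploratory analyses.

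**The concern.** The example in 9.1.1 is deaths. A patient dies at most once, so pooling deaths over ventilated days and using a Poisson variance is reasonable. DOT behave differently. One patient can contribute many, and the background in 2.2 shows the scale. A six-ICU case review reports that "antibiotics were not indicated in 59% of cases at the time of diagnosis, resulting in 1,183 days of unnecessary antibiotic use over 1 year", and the local review found that misdiagnosed patients "account for a median of 12 excess days of unnecessary antibiotics per patient". Days that arrive together in one patient are not independent events, which tends to make a Poisson standard error too small. Working the other way, if each treated day counts once, a patient's DOT cannot exceed the days ventilated. That bound makes the true variance smaller than Poisson when most days are treated.

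Section 9.2 declares significance for a stated hypothesis from this test, and the result enters the pilot's preliminary efficacy data (end of 2.2). If the standard error is wrong by an unknown amount in an unknown direction, a reader cannot interpret a p-value on either side of 0.05.

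**Working it through.** **What can be reproduced.** The documents give no sample size, event count, power or standard error for the DOT rates. The only stated figure is the 0.05 level, taken here as two-sided.

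**Evidence of dependence (2.2).** 0.59 × 231 = 136.3 cases, and 1,183 / 136.3 = 8.7 unnecessary days per case. The local median is 12 excess days per misdiagnosed patient.

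**The test as ordinarily read.** z = (r1 − r0) / √[r(1/D1 + 1/D0)], where r1 and r0 are the post and pre rates, r is the pooled rate and D1 and D0 are total ventilated days.

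**True variance over Poisson variance, one count per treated day.** V = (1 − p) × [1 + (Tw − 1)ρ]. Here p is the share of ventilated days treated, ρ the within-patient correlation, T a patient's ventilated days and Tw = E[T²]/E[T]. Actual two-sided error = 2 × [1 − Φ(1.96/√V)]. With T geometric and mean 6 days, Tw = 2 × 6 − 1 = 11:
- ρ = 0.5, p = 0.7: V = 0.3 × 6 = 1.80, error 14%.
- ρ = 0.2, p = 0.7: V = 0.3 × 3 = 0.90, error 4%.
- ρ = 0, p = 0.5: V = 0.5, error 0.6%.

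The Poisson standard error is right only at p = 1 − 1/[1 + (Tw − 1)ρ]. This is 0.44 for Tw 5 and ρ 0.2, 0.64 for Tw 10 and ρ 0.2, 0.82 for Tw 10 and ρ 0.5, and 0.88 for Tw 15 and ρ 0.5. The documents give neither Tw nor ρ.

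**Full-test simulation under no change.** All inputs are assumed: 2,500 pre and 500 post patients (the 5:1 ratio of years), mean ventilation 6 days, 4,000 trials per cell. Patients either have on/off courses or differ in their tendency to be treated. Each treated day counts as one DOT, or as 1–3 (mean 1.8) when concurrent agents count separately. On truly Poisson data the test rejected 5.4%. Otherwise, rejection (%) by share of days treated was:

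| Pattern | Count | 30% | 50% | 70% | 80% |
|---|---|---|---|---|---|
| 4-day courses | one | 20.2 | 7.7 | 0.2 | 0.0 |
| 4-day courses | 1–3 | 39.4 | 28.1 | 14.1 | 9.4 |
| 7-day courses | one | 28.3 | 16.5 | 2.2 | 0.1 |
| 7-day courses | 1–3 | 49.1 | 38.7 | 25.7 | 17.9 |
| Patients differ, ρ 0.2 | one | 17.6 | 10.3 | 4.1 | 0.9 |
| Patients differ, ρ 0.2 | 1–3 | 40.2 | 35.4 | 31.8 | 29.1 |
| Patients differ, ρ 0.5 | one | 33.3 | 25.0 | 14.2 | 7.1 |
| Patients differ, ρ 0.5 | 1–3 | 54.4 | 48.8 | 41.8 | 36.9 |

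With a patient-clustered variance, Σ(yᵢ − r·dᵢ)²/D² in each period (yᵢ and dᵢ are a patient's DOT and ventilated days), rejection was 4.3–5.9% in every cell run.

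**Second set of assumptions.** Ventilation lognormal with median 4 days and log-SD 0.7 or 1.0, with on/off courses:
- One agent, 60% of days, 8.7- or 12-day courses: V 1.4–2.1, error 10–18%.
- One agent, 50% of days, 3.5-day courses: V about 1.0, error about 5–6%.
- Two agents in 10% of 3.5-day courses, counted separately, 70% of days: V 0.64–0.70, error 1.4–1.9%.
- 1–3 agents, 30% of days, 12-day courses, log-SD 1.0: error about 56% by formula.

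Sample size does not drive the result. With 150, 300 and 600 post patients the error was 28, 30 and 29% (1–3 agents, 70% of days, 8.7-day courses, log-SD 0.85).

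**The case against.** **Poisson variance is a reading.** The plan names no variance, and a z-test can use a patient-level standard error. This stands, and the point is conditional on it. If another variance was intended, 9.2 should say so, and the request is the same.

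**The 2.2 figures are not course lengths.** They are unnecessary or excess days among misdiagnosed cases, not courses among all ventilated patients. Total days over cases does not show continuous runs, and if concurrent agents were already counted separately, adding more agents on top counts them twice. The 70% of patients on antibiotics in 2.2 is an external point prevalence, not a share of ventilated days. All of this stands. The figures show that DOT come in multiples per patient. They cannot calibrate the size of the error.

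**Section 9.3 already handles it.** The negative binomial model allows for extra variation between patients, and the monthly series does not use a count-based variance. Both will sit beside the 9.2 result, which is partial mitigation. Both are exploratory, so neither sets the significance that 9.2 declares.

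**Stronger readings that the documents do not support.** A reader might infer that the test overstates significance for antibiotic reductions. With one count per treated day it can equally be conservative, and one scenario with concurrent agents counted separately was conservative too. A reader might also look for a switch at about half of days treated. The break-even share moves with within-patient correlation and ventilation length, neither of which is given.

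**Conclusion.** The point holds in this form: on the ordinary pooled-Poisson reading, the 9.2 standard error is not valid for total and broad-spectrum DOT. Direction and size cannot be settled from the documents. They depend on how concurrent agents are counted, course length, the share of ventilated days treated, differences between patients, and ventilation length. With agents counted separately the standard error was too small in most scenarios, but not in all.

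The range of near 0% to about 55% describes the assumed scenarios. It is neither an estimate for this trial nor a ceiling: with longer, more skewed ventilation (Tw about 21), ρ 0.5, 1–3 agents and 30% of days treated, V is 18 and the formula gives 64%.

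Severity is modest. The endpoints are secondary in a single-arm pilot, the halting rule in 9.4.1 uses safety outcomes only, and no decision rule uses this p-value. Deaths are not affected.

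**What to change.** In 9.1.1 and 9.2, for the two DOT endpoints:
- Keep the pooled rate as the quantity compared.
- Use a patient-clustered or patient-bootstrap standard error. Alternatively, fit a quasi-Poisson regression of patient DOT counts with a log ventilator-day offset, a pre/post term and robust variance.
- Report the rate ratio with a two-sided 95% confidence interval.
- State whether concurrent agents count separately. This also settles what the endpoint means, which no variance method can do.

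Deaths may keep the z-test.

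The cost is SAP wording: 9.3 already requires each subject's DOT and ventilator days. The downside is that intervals will often be wider, by √2.1 = 1.4 to √4.8 = 2.2 times at variance ratios of 2.1 to 4.8, so fewer antibiotic results may be significant. Where the ratio is below 1 they will be narrower.

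The change does not address secular trend over the 2017–22 control period. The unadjusted pre/post comparison would still not isolate the intervention.
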